# 1.0 Objectives

1.1 Purpose: This will be a single site, 24-week double-blind, randomized, placebocontrolled pilot and feasibility clinical trial designed to estimate the treatment effect and tolerability of lisdexamfetamine (Vyvanse™) for the treatment of severe obesity in children ages 6 to < 12 years. After careful screening, all eligible participants (n=44) will be randomized, 1:1, to either lisdexamfetamine plus lifestyle therapy or placebo plus lifestyle therapy for 24 weeks of intervention. Participants and their parent/guardian will attend 8 in-person and 6 virtual visits. Participants will undergo regular assessments of anthropometrics, blood pressure, heart rate, and side effects and interval assessments of body composition, bone age, Tanner stage, laboratory tests, and questionnaires.

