- Tolerability and Safety Outcomes. The feasibility of conducting the larger clinical trial will depend on whether or not participants can tolerate LDX at doses that are effective for inducing BMI reduction. We will define tolerability as being able to tolerate a dose of at least 30 mg daily (the recommended starting dose) for the duration of the study. Importantly we will also measure outcomes of children taking doses less than 30 mg daily (i.e., 20 mg or 10 mg) as this information will be important for informing the dosing of the larger, definitive trial. We anticipate that participants taking LDX will have side effects at the same rate as patients who take LDX for the treatment of ADHD, so we will not define tolerability as not having any side effects whatsoever. Rather, the parent/guardian and participant will subjectively decide if the side effects, if present, are severe enough to warrant discontinuation of the study medication or reducing the dose below 30 mg daily. From an objective standpoint, every two weeks during dose escalation and every 4 weeks for the remainder of the study we will administer the Barkley's Side Effect Rating Scale which was developed specifically to monitor side effects from psychostimulants. This questionnaire, completed by the parent/guardian (and sometimes with the child's help) requests feedback on 17 items on a 9-point Likert scale including typical physical side effects (e.g., decrease appetite, insomnia, stomachaches, and headaches) and behavioral symptoms (e.g., irritability, anxiety).78. Other measures of tolerability will include incidence of developing stage 1 hypertension and tachycardia, measured by blood pressure and heart rate. Stage 1 hypertension is defined as SBP and/or DBP >95th percentile on three separate occasions and will be confirmed by a 24hour ambulatory blood pressure monitor. Tachycardia in childhood is defined as heart rate > 120 bpm at rest measured on three separate occasions.80

PROTOCOL TITLE: Lisdexamfetamine for the Treatment of Severe Obesity in Children Aged

6 to 12 Years

VERSION DATE: 19Sep2025

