#### 14.0 Statistical Considerations

Data Analysis Plan: Descriptive analyses of baseline characteristics and outcomes will include means and standard deviations, median and range for continuous variables and frequencies with percentages for categorical variables. Safety analyses (including Barkley's Side Effect Rating Scale and incidence of hypertension and tachycardia) will be primarily descriptive reporting the number and percentage of adverse events during participation in the study. All safety outcomes will be evaluated and monitored throughout the study. Confidence intervals (Cis) and P-values for all analyses will be based on robust variance estimation. Statistical significance will be considered as p<0.05.

PROTOCOL TITLE: Lisdexamfetamine for the Treatment of Severe Obesity in Children Aged

6 to 12 Years

VERSION DATE: 19Sep2025

**Aim 1:** Estimate the treatment effect of LDX plus lifestyle therapy vs placebo plus lifestyle therapy on changes in BMI (%BMIp95 primary endpoint), body fat, cardiometabolic health and quality of life (QOL) from baseline to 24 weeks. **H1:** We hypothesize that LDX compared to placebo will result in a greater mean decrease in %BMIp95 and body fat, and improved cardiometabolic health and QOL at 24 weeks.

The primary outcome measurement will be absolute change in percent of the BMI 95th percentile abbreviated %BMIp95. Although we will report on other metrics of BMI change including absolute BMI change and percent BMI change, we chose %BMIp95 as the primary outcome measurement because of its clinical utility in measuring changes in BMI in young children who have severe obesity and a consensus in the research community that expressing BMI change relative to the 95th percentile is preferred over other metrics such as BMI standard deviation score a.k.a. z-score. The limitation of BMIz is explained by the flattening of BMIz curve at values significantly above the 95th percentile, despite the wide variance of BMIs in youth with severe obesity, which therefore leads to an underestimation of clinically significant improvement in weight status). The primary outcome will be the mean change in %BMIp95 from baseline to 24 weeks follow-up compared between treatment groups, while adjusting for baseline value for added precision. See Table 1 for examples of changes in BMI and corresponding changes in %BMIp95.

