**H2:** We hypothesize that at least 80% of participants will tolerate an LDX dose of ≥30 mg daily (recommended starting dose) for 24 weeks and that the LDX group compared to the placebo group will not demonstrate clinically significant increases in blood pressure or heart rate.

We will define feasibility to conduct the larger trial if, in this pilot study, >80% of participants randomized to LDX tolerate a dose of >30 mg daily, the recommended starting dose, for 24 weeks and there are no statistically significant differences between the LDX group and placebo group in incidence of developing stage 1 hypertension or tachycardia. Outcomes will be captured for all regardless of tolerability and will inform inclusions/exclusion criteria and dose escalation schedule for the subsequent trial. Safety outcomes will be monitored carefully and include instances of stage 1 hypertension (defined as SBP and/or DBP ≥95th percentile on 3 separate occasions) and confirmed by 24 hour ambulatory blood pressure monitor) and tachycardia (defined as heart rate ≥120 bpm at rest measured on 3 separate occasions). The Barkley Side Effect Rating Scale will also be measured at every 2 weeks during dose escalation and then every 4 weeks for the remainder of the study and will be used to help identify reasons for limited tolerability should this occur. Height velocity in cm/year will be determined by the difference in measured height between the baseline and 24-week assessments and will be used to calculate a height velocity SDS (z-score). Given the potential for LDX to disrupt sleep and the impact of sleep on obesity, participant sleep will be measured objectively using accelerometry with the ActiGraph (GT3X-BT) device, which has been shown to have acceptable reliability and validity in sleep-wake detection compared with laboratory-based polysomnography. Nighttime sleep efficiency, defined as the portion of time dedicated to sleep that is spent asleep, will be evaluated as the primary sleep endpoint of interest, with higher scores representing more efficient sleep. All indexes will be calculated using the ActiLife software. Participant mental health will be monitored by the Columbia-Suicide Severity Rating Scale (C-SSRS) and Children's Depressive Inventory-2 (CDI-2).

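### Robust-variance intervals, the only kind the plan names, do not suit the tolerability proportion in about 22 LDX children, and a pass on the >80% rule should be reported with an exact or Wilson interval

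*Combined protocol and SAP*

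**What the plan says.** Section 1.0 gives the size and allocation: "all eligible participants (n=44) will be randomized, 1:1, to either lisdexamfetamine plus lifestyle therapy or placebo plus lifestyle therapy". That is about 22 children on LDX.

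Section 14.0 (Aim 2) states H2: "We hypothesize that at least 80% of participants will tolerate an LDX dose of ≥30 mg daily". It then sets a two-part feasibility definition. The tolerability part is "We will define feasibility to conduct the larger trial if, in this pilot study, >80% of participants randomized to LDX tolerate a dose" at the stated level for 24 weeks. The safety part is that "there are no statistically significant differences between the LDX group and placebo group in incidence of developing stage 1 hypertension or tachycardia". No interval, unacceptable rate or error rate is attached to the 80% comparison.

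On intervals, the opening paragraph of Section 14.0 says that confidence intervals and p-values "for all analyses will be based on robust variance estimation". No other interval method appears anywhere. The same paragraph describes the safety analyses as mainly descriptive.

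The dose cut-off is written in two ways. Section 4.2 says "We will define tolerability as being able to tolerate a dose of at least 30 mg daily (the recommended starting dose) for the duration", and H2 uses the same inclusive boundary. The feasibility sentence in Section 14.0 reads as strictly more than 30 mg.

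**The concern.** Aim 2 is an estimation aim, and its main quantity is one proportion from one small arm. The hoped-for result is near the upper end of the scale, where intervals of the form estimate ± 1.96 standard errors behave worst. Followed literally, the plan would attach an interval that is too narrow, can exceed 100%, and vanishes if every child tolerates the drug.

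Two conclusions could then go wrong. A high result such as 21/22 would appear to show that at least 80% tolerate the dose when a valid interval does not. A bare pass of the rule, with no usable interval beside it, could also be read as confirming H2. Section 4.2 makes feasibility of the larger trial depend on whether children tolerate the drug, so the precision of this estimate should be shown correctly.

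**Working it through.** **Inputs.** n = 22 on LDX (44 randomised 1:1, Section 1.0). Threshold: observed proportion above 80% (Section 14.0). The plan gives no figure of its own for precision or error rates, so there is none to reproduce.

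**1. The rule as a count.** 17/22 = 77.3% and 18/22 = 81.8%, so the limb is met at 18 or more. At n = 22, above 80% and at least 80% give the same count.

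**2. What robust variance gives for one proportion.** In an intercept-only model on the natural scale the sandwich variance is p̂(1 − p̂)/n, which gives the Wald interval p̂ ± 1.96·√[p̂(1 − p̂)/n].
- 18/22: 0.818 ± 1.96 × 0.0822 = 0.657 to 0.979
- 21/22: 0.955 ± 1.96 × 0.0444 = 0.867 to 1.042
- 22/22: the standard error is 0, so 1.000 to 1.000

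**3. Comparison with valid intervals.** The exact (Clopper-Pearson) limits are beta quantiles. At 22/22 the lower limit reduces to 0.025^(1/22) = 0.846. The Wilson lower limit at 22/22 is 22/(22 + 1.96²) = 22/25.84 = 0.851.

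| Result | Wald | Exact | Wilson |
|---|---|---|---|
| 18/22 | 66-98% | 60-95% | 61-93% |
| 21/22 | 87-104% | 77-99.9% | lower limit 78% |
| 22/22 | 100-100% | 85-100% | 85-100% |

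At 21/22 the Wald lower limit is above 80%, while the exact and Wilson limits are below it. This is the one passing count at which the choice of method changes what can be said about H2. At 18/22 all three lower limits are below 80%. At 22/22 all three are above it, but the Wald interval claims certainty.

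**4. Actual coverage of the nominal 95% Wald interval, n = 22.** Sum the binomial probabilities of the counts whose interval contains the true rate.
- True 85%: counts 15 to 20 qualify. 0.0255 + 0.0631 + 0.1262 + 0.1987 + 0.2370 + 0.2015 = 0.852.
- True 95%: counts 18 to 21 qualify. 0.0182 + 0.0726 + 0.2070 + 0.3746 = 0.672. The result 22/22, with probability 0.95²² = 0.324, misses because its interval has no width.

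**5. Context: how often the tolerability limb is met.** P(X ≥ 18) for X ~ Binomial(22, p):

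| True rate | 60% | 70% | 80% | 85% | 90% | 95% |
|---|---|---|---|---|---|---|
| P(limb met) | 2.7% | 16.5% | 54.3% | 77.4% | 93.8% | 99.6% |

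Only 80% comes from the plan; the other rates are illustrative. The hypertension and tachycardia limb can only lower these chances. The realised arm size matters too: for 20 to 24 children, the chance of missing the limb at a true 80% is 41-59%, and of meeting it at a true 70% is 11-20%.

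**The case against.** **The Wald reading is partly an inference.** No sentence assigns a Wald interval to tolerability. Safety analyses are mainly descriptive, and where Section 14.0 describes a method for specific endpoints (the Exploratory Aim) it applies robust variance to differences in mean change. This stands as a limit on the point. Still, the sentence covers all analyses and nothing replaces it for this proportion. Moving to the logit scale would keep the limits inside 0-100%, but the estimate is infinite at 22/22, so the problem remains there.

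**This is a pilot.** Section 14.0 says the sample size is not driven by a power analysis. That is accepted: the point asks for no power calculation, more children or different threshold.

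**Stronger readings that the documents do not support:**
- *The rule is close to a coin toss and would stop the programme.* The 46% chance of missing the limb at a true 80% (1 − 0.543) is about what any point-estimate cut-off gives when the truth lies on the threshold, and better reporting does not change it. Section 14.0 defines feasibility. It writes no termination, and it has a second limb.
- *The data cannot separate 60% from 95% tolerability.* That is the exact interval at one outcome, 18/22. The rule itself is met with probability 2.7% at 60% and 99.6% at 95%.
- *The larger trial's dosing and retention would rest on this one figure.* Section 14.0 captures outcomes whether or not the drug is tolerated, and Section 4.2 measures outcomes at lower doses to inform dosing. Under Section 3.3, a child who stops drug because the smallest dose is not tolerated remains in the trial, so retention is a separate quantity.
- *A pass should require the lower limit to exceed 80%.* That would need 22/22, with probability 0.90²² = 9.8% at a true 90% and 32% at 95%. It is a confirmatory standard that an estimation aim does not call for.

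**Conclusion.** The point holds as a defect in the interval method and in how a pass would be worded. It is not a defect in having a planning threshold. The stated method is unsuitable for a single proportion near 100% in about 22 children: coverage is about 85% at a true 85% and 67% at a true 95%, width is zero at 22/22, and at 21/22 the lower limit is 87% where the exact limit is 77%. A minimal pass of 18/22 has an exact interval of 60-95%, so meeting the threshold does not show that at least 80% tolerate the drug.

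This assumes that the LDX arm is 22, that every child randomised to LDX is classified as tolerating or not, and that robust variance is applied on the natural scale. Severity is minor to moderate.

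The >30 mg and ≥30 mg definitions also conflict. A child whose dose stays at exactly 30 mg counts under H2 and Section 4.2 but not under the feasibility sentence as it reads. The sign may be typographic, but the proportion is undefined until the sections agree.

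**What to change.** 1. Reconcile the >30 mg and ≥30 mg wording across Sections 3.2, 4.2 and 14.0 before the proportion is computed.
2. In Section 14.0, exempt single-arm proportions from the robust-variance sentence, and name either the Wilson or the Clopper-Pearson 95% interval for tolerability.
3. Use the actual number randomised to LDX as the denominator, not an assumed 22.
4. Keep the >80% planning threshold. Report it as planning threshold met or not met, x% (95% CI), and do not present a pass as proof that at least 80% tolerate the drug.

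The pass probabilities may be shown as background, but they change no result.

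The cost is a few lines of SAP text, with no new data, visits or participants. The downside is a wider and less favourable interval: at 21/22, for example, the lower limit falls from 87% to 77% (exact) or 78% (Wilson).

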### 3.0 Study Endpoints/Events/Outcomes

- 3.1 Primary Endpoint/Event/Outcome: To estimate the treatment effect of LDX + lifestyle therapy vs. placebo + lifestyle therapy on changes in BMI (%BMIp95), body fat, cardiometabolic health and quality of life (QOL) from baseline to 24 weeks. We hypothesize that LDX compared to placebo will result in a greater mean decrease in %BMIp95 and body fat, improved cardiometabolic health and QOL at 24 weeks.
- 3.2 Secondary Endpoint(s)/Event(s)/Outcome(s): To generate estimates of the tolerability and safety of LDX used for the treatment of severe obesity in children. We hypothesize that at least 80% of participants will tolerate an LDX dose of at least 30 mg per day (the recommended starting dose) and that the LDX group compared to the placebo group will not demonstrate clinically significant increases in blood pressure or heart rate.

PROTOCOL TITLE: Lisdexamfetamine for the Treatment of Severe Obesity in Children Aged

6 to 12 Years

VERSION DATE: 19Sep2025

We will also examine the potential mechanisms by which LDX affects BMI in children with obesity, including its effect on executive functioning, reward processing, appetite, resting energy expenditure, and health behaviors (diet, eating behaviors, and physical activity). Study Intervention(s)/Investigational Agent(s)

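### The feasibility rule in Section 14.0 reads >30 mg where H2, Section 4.2 and Section 3.2 include exactly 30 mg: check the sign in the source and, if it stands, reconcile the four statements

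*Combined protocol and SAP*

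**What the plan says.** Four statements in the combined protocol and SAP set the tolerability threshold.

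- **Section 14.0, Aim 2, feasibility rule.** The larger trial is feasible if more than 80% of "participants randomized to LDX tolerate a dose of >30 mg daily, the recommended starting dose, for 24 weeks", and if the arms do not differ significantly in stage 1 hypertension or tachycardia.
- **Section 14.0, Aim 2, H2.** The hypothesis is that "at least 80% of participants will tolerate an LDX dose of ≥30 mg daily (recommended starting dose) for 24 weeks".
- **Section 4.2, Tolerability and Safety Outcomes.** "We will define tolerability as being able to tolerate a dose of at least 30 mg daily", for the duration of the study. The family's decision that counts against tolerability is whether side effects are "severe enough to warrant discontinuation of the study medication or reducing the dose below 30 mg daily".
- **Section 3.2, secondary endpoint.** The expectation is that at least 80% will "tolerate an LDX dose of at least 30 mg per day".

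Section 3.3 starts every child at 30 mg for 2 weeks. Titration is not forced, the dose is held at the maximum tolerated one, and it can be stepped down by 10 mg for intolerance.

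**The concern.** The feasibility rule is the only place where tolerability becomes a decision. Section 14.0 says that the sample size is not driven by a power analysis and that the purpose is to inform a larger study, so this sentence carries much of what the pilot will be used for. If its strict sign is genuine, the rule classifies children at exactly 30 mg differently from the endpoint definition that it is meant to apply.

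The boundary dose is not a remote case. It is the starting dose, and a child who cannot move up from it, or who steps back to it, may be held there. With only 22 children on LDX, the classification of two or three of them can decide whether the rule is met. If the wording is left open until the dose distribution is known, the threshold could be chosen after seeing which reading passes.

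**Working it through.** **Thresholds compared**

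| Place | Threshold | Child held at exactly 30 mg |
|---|---|---|
| Section 3.2 | at least 30 mg | success |
| Section 4.2 | at least 30 mg; a reduction below 30 mg counts against | success |
| Section 14.0, H2 | ≥30 mg | success |
| Section 14.0, feasibility rule | >30 mg | failure |

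**Can the strict rule be met as written?** It asks for more than 30 mg for 24 weeks. Section 3.3 gives every child 30 mg for the first 2 weeks. Read literally, no child qualifies. The strict sign can be applied only by reinterpreting it, for example as the dose at which the child is maintained after escalation. The figures below use that softer reading.

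**Inputs.** Section 1.1 randomizes 44 children 1:1, so 44 / 2 = 22 are on LDX. The plan states no operating characteristics for the rule, so there is no figure to reproduce.

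**Count needed.** 0.80 × 22 = 17.6. Since 17/22 = 77.3% and 18/22 = 81.8%, 18 children are needed under both percentage wordings, more than 80% and at least 80%. The two wordings part only when 80% of the denominator is a whole number: 16 against 17 of 20, or 20 against 21 of 25.

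**Chance of reaching 18.** Treat children as independent, with X the number of successes:

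P(X ≥ 18) = Σ (k = 18 to 22) C(22, k) p^k (1 − p)^(22 − k)

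Example at p = 0.90, written as 0 to 4 failures: 0.0985 + 0.2407 + 0.2808 + 0.2080 + 0.1098 = 0.938.

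Let t be the true proportion who tolerate 30 mg or more, and s the proportion of all children who stay at exactly 30 mg. The inclusive reading has p = t; the strict reading has p = t − s. Both t and s are assumptions, since the documents give neither.

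| t | Inclusive | Strict, s = 5% | Strict, s = 10% |
|---|---|---|---|
| 80% | 0.543 | 0.323 | 0.165 |
| 85% | 0.774 | 0.543 | 0.323 |
| 90% | 0.938 | 0.774 | 0.543 |
| 95% | 0.996 | 0.938 | 0.774 |

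Ten percent of 22 is 2.2 children, so the last column corresponds to about two children at the boundary dose.

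**The case against.** The strongest reply is that the strict sign is an artefact of reading the PDF.

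- Section 7.2 preserves one inclusive sign as an underlined > in the tachycardia criterion, so the file does use that form.
- Section 4.2 prints a strict sign for the 95th blood-pressure percentile and for 120 bpm, where Section 14.0 prints ≥ for the same two definitions.
- In the disputed sentence, the 80% sign and the 30 mg sign both differ from H2 in the same way, which lost underlines would explain together.
- The sentence glosses 30 mg as the starting dose, which fits an inclusive threshold better, and the strict reading cannot be met for 24 weeks.

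This is a live explanation, and it is why the source must be checked first. It is not established, however: ≥ survives three times in the Aim 2 text itself, for H2, the 95th percentile and 120 bpm.

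It can also be said that Section 4.2 is the explicit definition, so an analyst would follow it, and that outcomes are captured at every dose, so either classification can be computed later. Both are fair and limit the harm. They do not tell the reader which criterion governs the decision.

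Three stronger readings are tempting, and the documents do not support them.

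- A reader might infer that the sponsor means to require more than the starting dose. Nothing beyond the single sign says so.
- A reader might infer that some children are expected to remain at exactly 30 mg. Section 3.3 makes this possible but gives no rate.
- A reader might treat the mismatch between more than 80% and at least 80% as a second error with consequences. At 22 it changes nothing.

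**Conclusion.** The point holds conditionally. As the text stands, the decision rule and the endpoint definition disagree about children at exactly 30 mg, and the rule cannot be applied literally. If the source PDF shows ≥, the disagreement about dose disappears and only the percentage wording is left to align.

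If > stands, the effect could be material. With 10% of children at exactly 30 mg, the chance of meeting the tolerability condition falls by 0.22 to 0.45 across assumed true tolerability of 85% to 95% (0.774 − 0.323 = 0.451; 0.938 − 0.543 = 0.395; 0.996 − 0.774 = 0.222). These figures rest on assumed rates, independence between children, exactly 22 on LDX with all of them in the denominator, and reading the strict sign as the maintained dose. They are not probabilities of a decision to go ahead, because the rule's hypertension and tachycardia condition is left out.

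**What to change.** 1. Check the sign in the feasibility sentence against the source document.
2. If > is genuine, reconcile Section 3.2, Section 4.2, H2 and the feasibility rule so that all four state one identical criterion. The choice of threshold is the sponsor's. State also whether it refers to the maintained dose or to every week of treatment, since the first 2 weeks are at 30 mg for everyone.
3. Align the percentage wording at the same time. Adding the count (18 of 22 at the planned size) would be a helpful clarification, though not a necessary one.
4. Do this before unblinding and before dose distributions by arm are seen.

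The cost is one symbol and one phrase in Section 14.0, with matching wording in Sections 3.2 and 4.2 if needed. No procedure, visit or sample size changes.

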# A.5. Tolerability of LDX for the treatment of severe obesity in children is unknown

Although psychostimulants, including LDX, have a long-standing, well-established safety profile,  the relative tolerability of these medications in children who do not have ADHD has yet to be established. Aside from decreased appetite, the most common side effects of psychostimulants in children with ADHD include insomnia, upper abdominal pain, and irritability. Particularly relevant to patients with obesity are the impact of psychostimulants on blood pressure, heart rate and linear growth, the effects of which tend to be dose dependent in children with ADHD.  Clinical trials of LDX for the treatment of ADHD in children report

PROTOCOL TITLE: Lisdexamfetamine for the Treatment of Severe Obesity in Children Aged

6 to 12 Years

VERSION DATE: 19Sep2025

[figure not shown]
mean increases in systolic blood pressure of 2-4 mm Hg and in heart rate of 3-7 bpm. The clinical significance of this effect on the cardiovascular system is uncertain, especially for children with obesity who may be at higher risk of having underlying cardiovascular impairment such as hypertension. Importantly, in adults with obesity treated with phentermine, also a noradrenergic agent, blood pressure tends to decrease as a function of weight loss. 12 Thus, measuring the impact of LDX on blood pressure and heart rate in children with obesity is critical for assessing its utility as an adjunct treatment for obesity in this population. Regarding linear growth, psychostimulants have been shown to have adverse effects on height velocity at various stages of childhood, including prepuberty. 13,14 However, final adult height does not appear to be impacted. 15 Similarly, obesity can effect growth and has been associated with taller stature during childhood but decreased growth velocity in adolescence; the net result again is no association between childhood weight status and adult height. 16 That said, as both psychostimulant use and obesity can affect growth velocities during the pre- and peri-pubertal periods, the net effect of both of these simultaneously during this stage of development is unclear and warrants further investigation.

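### The safety limb of the feasibility definition has no direction, so significantly fewer hypertension or tachycardia cases on LDX would also fail it, although H2 concerns only increases (minor)

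*Combined protocol and SAP*

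**What the plan says.** Section 14.0, Aim 2, sets the go/no-go condition. Its first limb is tolerability: "We will define feasibility to conduct the larger trial if, in this pilot study, >80% of participants randomized to LDX tolerate a dose" (a dose threshold and the 24-week period complete it). Its second limb is safety: "there are no statistically significant differences between the LDX group and placebo group in incidence of developing stage 1 hypertension or tachycardia". The two limbs are joined by *and*, so both must hold.

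The hypothesis just above it points one way only. H2 expects that the LDX group, against placebo, "will not demonstrate clinically significant increases in blood pressure or heart rate". Section 3.2 says the same of the LDX group compared to "the placebo group will not demonstrate clinically significant increases in blood pressure or heart rate".

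On testing, Section 14.0 says "Statistical significance will be considered as p<0.05" and does not say whether tests are one- or two-sided. It adds that "P-values for all analyses will be based on robust variance estimation", but the same paragraph says that safety analyses, including incidence of hypertension and tachycardia, "will be primarily descriptive reporting the number and percentage of adverse events during participation in the study". It names no test for comparing incidence. No other section limits the safety limb to an excess of cases on LDX.

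**The concern.** A safety condition attached to a hypothesis of no increase should fail only on evidence of an increase. A condition phrased as no significant difference fails in both directions. If placebo children developed significantly more hypertension or tachycardia than LDX children, the literal answer would be that feasibility is not met, for a reason unrelated to harm.

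The background mentions a route to that result for blood pressure: in adults with obesity on phentermine, "blood pressure tends to decrease as a function of weight loss". H1 also hopes for better cardiometabolic health on LDX. What is at stake is a prespecified rule that could return the wrong answer. The team would then have either to follow it or to reinterpret it after seeing unblinded data.

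**Working it through.** The plan gives no error rate, power or incidence for this rule, so there is no stated figure to reproduce.

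**Inputs**
- 44 children randomised 1:1 (Section 1.1), so 22 per arm, all assumed evaluable.
- Significance at p<0.05 (Section 14.0). Two-sided is assumed because the rule speaks of differences and names no direction.
- Test: not named. Two candidates are used: Fisher's exact test, and the risk difference with unpooled variance, which is one way to apply the general robust-variance statement.
- True incidence in each arm: not given. The values below are assumptions for illustration.

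**Step 1. Smallest result that fails in LDX's favour (x cases on LDX, y on placebo)**

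Fisher with x = 0: p = 2 × C(22,y) / C(44,y).
- y = 4: 2 × 7,315 / 135,751 = 0.108, not significant.
- y = 5: 2 × 26,334 / 1,086,008 = 0.048, significant.

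Unpooled risk difference with x = 0: z = q / √(q(1−q)/22), where q = y/22.
- y = 3: 0.136 / 0.073 = 1.86, p = 0.062, not significant.
- y = 4: 0.182 / 0.082 = 2.21, p = 0.027, significant.

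With 1 case on LDX, placebo needs 7 (Fisher) or 6 (unpooled).

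**Step 2. Chance of such a result, per endpoint**

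Sum Bin(x; 22, p_LDX) × Bin(y; 22, p_placebo) over all of the 23 × 23 tables with x < y and p<0.05.

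| Assumed LDX | Assumed placebo | Fisher | Unpooled |
|---|---|---|---|
| 2% | 2% | <0.01% | 0.06% |
| 5% | 5% | 0.13% | 0.74% |
| 10% | 10% | 0.72% | 2.2% |
| 20% | 20% | 1.2% | 2.7% |
| 10% | 5% | 0.04% | 0.23% |
| 5% | 10% | 2.2% | 6.3% |
| 10% | 20% | 8.4% | 15% |
| 5% | 20% | 20% | 33% |

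The limb names two endpoints. If either can fail it, the combined chance is at most the sum of the two. At 5% in every arm that is at most 2 × 0.13% = 0.26% (Fisher) or 2 × 0.74% = 1.48% (unpooled).

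**Step 3. The same rule in the harmful direction**

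Summing instead over x > y, LDX 20% against placebo 5% is detected with probability 20% (Fisher) or 33% (unpooled).

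**Step 4. Effect of making the limb directional**

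Count only the upper tail of the two-sided 0.05 test, equivalent to one-sided 0.025. Every table with x < y then passes, so failures in the favourable direction are 0. With equal arms the set of tables that fail with x > y does not change, so detection at 20% against 5% stays at 20% / 33%.

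The threshold has to be written down. If *significantly higher* were taken as one-sided 0.05, Fisher detection at the same rates would be 26%, which is a different rule.

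**The case against.** The strongest reply is that the problem will hardly ever arise.
- For children with ADHD, the background reports mean rises on LDX of 2-4 mm Hg in systolic pressure and 3-7 bpm in heart rate. The remark about falling pressure concerns another drug, in adults, and blood pressure only. It offers no route to fewer tachycardia cases on a stimulant.
- Section 7.2 excludes children with hypertension or tachycardia at entry. Both outcomes need three separate occasions, and hypertension also needs ambulatory confirmation, all within 24 weeks. A placebo incidence near 20% is hard to reach.
- The limb follows directly after H2, so an excess on LDX is the evident intent.

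All of this stands and limits the point to minor severity. It does not remove it, because the operative sentence still says something other than what was meant.

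Three stronger readings are tempting, and the documents do not support them.
- *The rule would stop the programme because the drug protects.* Section 14.0 defines feasibility but attaches no automatic consequence. It says outcomes will inform the next trial's design, and stopping of the study is handled separately in Section 17.
- *The rule fails far more than 5% of the time when LDX causes no increase.* That needs a strongly protective effect. At the equal rates tabulated, the favourable tail is at most 2.7%.
- *The plan prescribes the unpooled test, so the larger figure in each pair applies.* No test for incidence is named, and safety analyses are called primarily descriptive.

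**Conclusion.** The point holds on the wording. The safety limb is two-directional, the hypothesis it serves is one-directional, and nothing elsewhere reconciles them. Significantly fewer cases on LDX would literally leave the feasibility definition unmet.

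The size is minor. In likely settings the chance per endpoint runs from well under 1% to about 6%, and it becomes material only if LDX sharply lowers an already high incidence. These figures rest on 22 evaluable children per arm, a two-sided 0.05 test and assumed incidence rates. The wording finding rests on none of those probabilities.

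The more consequential weakness of the same sentence is separate: with 22 per arm, absence of significance is taken as evidence of safety, although a rise from 5% to 20% would be missed about 67% to 80% of the time (100% minus 33% or 20%). Correcting the direction does not touch that.

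**What to change.** In the feasibility definition under Aim 2, Section 14.0, replace the no-difference condition with: *the incidence of stage 1 hypertension or tachycardia is not significantly higher in the LDX group than in the placebo group (upper tail of the two-sided 0.05 test, i.e. one-sided 0.025)*. Name the test used for incidence. State that a lower incidence on LDX is reported but does not count against feasibility.

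If the limb is instead recast as a confidence limit, which would also be the place to address the low power, only the upper limit for LDX minus placebo should count.

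The cost is one phrase in Section 14.0, to be settled before unblinding. It needs no new data, participants or procedures and gives up no ability to detect harm.
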